### **Drug interactions**

Sodium picosulfate and its active metabolite are not absorbed to any significant degree and there is no evidence of direct, time dependent or metabolism dependent inhibition on the major drug metabolizing cytochrome P450 enzymes in human liver microsomes and hepatocytes.

Some medicines (e.g. tetracycline and fluoroquinolone antibiotics, iron, digoxin, chlorpromazine and penicillamine) have the potential to chelate with magnesium.

#### **1.2.2 Clinical Safety Data**

Up to May 2019, the cumulative number of subjects from completed clinical trials, for Compound Sodium Picosulfate Granules, is estimated to 1,974 subjects.

The key efficacy, safety results and exposures to investigational drug from the completed Ferring sponsored Phase 3-4 clinical trials are presented in the table below.

Trial Code/Phase	Trial Design	Country	Compound Sodium Picosulfate Granules Dose/Schedule	No. of Subjects	Results
2009-01 (Phase 3)	Multicentre, randomized, assessor-blinded, active control, parallel-group	US	Split-day a	Compound Sodium Picosulfate Granules: 305; HalfLyte: 298; Total: 603	Compound Sodium Picosulfate Granules superior to HalfLyte in overall colon cleansing (Aronchick Scale). No drug-related safety concerns or novel adverse events were observed. No clinically meaningful changes in laboratory tests, ECGs, or physical examinations, including multiple orthostatic pulse and blood pressure measurements were observed. The safety profile supported a positive benefit/risk ratio.
2009-02 (Phase 3)	Multicentre, randomized, assessor-blinded, active	US	Day-before b	Compound Sodium Picosulfate Granules: 296;	Compound Sodium Picosulfate Granules non-inferior to HalfLyte in overall colon cleansing (Aronchick Scale). No drug-related safety concerns or novel adverse

## Non-Interventional Study (NIS) Protocol

Trial Code/Phase	Trial Design	Country	Compound Sodium Picosulfate Granules Dose/Schedule	No. of Subjects	Results
	control, parallel-group			HalfLyte: 302; Total: 598	events were observed. No clinically meaningful changes in laboratory tests, ECGs, or physical examinations, including multiple orthostatic pulse and blood pressure measurements were observed. The safety profile supported a positive benefit/risk ratio.
999169 CS2 (Phase 3)	Multicentre, randomized, assessor-blinded, active control, parallel-group	China	Split-day c	Compound Sodium Picosulfate Granules:150; PEG-ELS:150; Total: 300	Compound Sodium Picosulfate Granules non-inferior to PEG-ELS (polyethylene glycol 4000-electrolyte powder for oral solution) in overall bowel cleansing (Ottawa Scale), cleansing of each colon section, and overall fluid retention. There were no clinically significant differences in changes from baseline to post-treatment in clinical safety laboratory values, vital signs, ECG parameters, or physical examination findings. Compound Sodium Picosulfate Granules was superior to PEG-ELS in subject-rated outcomes.
000121 (Phase 3)	Multicentre, randomized, assessor-blinded, parallel-group	EU	Split-dose d vs. Day-before e	Split-dose: 73; Day-before: 131; Total:204	Subjects receiving the tailored schedule had 7-9 times greater odds of being a responder (Ottawa Scale) with regard to colon cleansing status when compared with day-before schedule. Subject convenience and satisfaction (ease of consuming, overall experience, taste, willingness and acceptance to use for future colonoscopy) were high for each schedule. No new safety signals were seen with either schedule.
000176 (Phase 3)	Multicentre, randomized, assessor-blinded, active control, parallel-group	Japan	Split-day f vs. Day-before b	Compound Sodium Picosulfate Granules Split-day: 214; Compound Sodium Picosulfate Granules Day-before: 212;	Results showed that both Compound Sodium Picosulfate Granules dosing schedules were non-inferior to Niflec, as judged by an Independent Central Judging Committee (Japanese Colon Cleansing Scale). Subjects considered Compound Sodium Picosulfate Granules more acceptable than Niflec, according to a questionnaire administered on the day of colonoscopy. No new safety

## Non-Interventional Study (NIS) Protocol

Trial Code/Phase	Trial Design	Country	Compound Sodium Picosulfate Granules Dose/Schedule	No. of Subjects	Results
				PEG-ELS: 211; Total: 637	signals were seen with either schedule.
000253 (Phase 3)	Multicentre, randomized, assessor-blinded, active control, parallel-group	US	Split-day a	Compound Sodium Picosulfate Granules: 453; Sodium picosulfate, magnesium oxide, and anhydrous citric acid pre-mixed oral solution: 448; Total: 901	The Sodium picosulfate, magnesium oxide, and anhydrous citric acid pre-mixed oral solution treatment demonstrated statistically significant superiority over Compound Sodium Picosulfate Granules for the primary endpoint and the key secondary endpoint. Overall, the safety results did not indicate any safety concerns or signals for either bowel preparation.
000180 (Phase 4)	Multicentre, randomized, assessor-blinded, active control, parallel-group	Brazil	Split-day a	Compound Sodium Picosulfate Granules: 90; Mannitol/Bisacodyl: 89; Total: 179	Results showed that Compound Sodium Picosulfate Granules is a tolerable and safe preparation for colon cleansing in preparation for a colonoscopy in adult subjects, but the objective of demonstrating superior efficacy over the active control was not achieved.

a: Split-day schedule: On the day before colonoscopy, first dose between 5:00 pm and 9:00 pm; on the day of colonoscopy, second dose approximately 5 hr before but no more than 9 hr prior to the procedure.

b: Day-before schedule: On the day before colonoscopy, one dose between 4:00 pm and 6:00 pm and another dose 6 to 8 hr later between 10:00 pm and 12:00 am.

c: Split-day schedule: On the day before colonoscopy, first dose between 8:00 pm and 9:00 pm; on the day of colonoscopy, second dose 4 to 6 hr before colonoscopy.

d: Split-dose schedule: First dose 10 to 18 hr before colonoscopy and second dose 4 to 6 hr before colonoscopy.

e: Day-before schedule: On the day before colonoscopy, one dose prior to 8:00 am and another dose 6 to 8 hr later.

f: Split-day schedule: On the day before colonoscopy, first dose between 5:00 pm and 9:00 pm; on the day of colonoscopy, second dose at least 4 and up to 9 hr prior to colonoscopy.

\* HalfLyte: (Powder: PEG-El (polyethylene glycol electrolyte solution) 3350/Sodium Chloride/Sodium Bicarbonate/KCL) and Bisacodyl Tablets Bowel Prep Kit.

In randomized, multicentre, controlled clinical trials, nausea, headache, and vomiting were the most common adverse reactions (>1%) following Compound Sodium Picosulfate Granules administration. Since abdominal bloating, distension, pain/cramping, and watery diarrhoea are known

to occur in response to bowel cleansing preparations, these effects were documented as adverse events in the clinical trials only if they required medical intervention (such as a change in study drug or led to study discontinuation, therapeutic or diagnostic procedures, met the criteria for a serious adverse event), or showed clinically significant worsening during the study that was not in the frame of the usual clinical course, as determined by the investigator.

Limitations in respect to populations typically under-represented in clinical trial development programmes are presented as follows:

Paediatric population	In completed Ferring sponsored clinical trial for the paediatric population (000103), a total of 78 paediatric subjects were included (48 paediatric subjects were randomised to Compound Sodium Picosulfate Granules and 30 to PEG). The subjects were randomised to one of the treatment arms by age groups from 9-12 years and 13-16 years. The Compound Sodium Picosulfate Granules age group 9-12 years received either 1/2 sachet x 2 or 1 sachet x 2, whilst the Compound Sodium Picosulfate Granules age group 13-16 years received 1 sachet x 2. The results of the trial demonstrated that the '1 sachet x 2 dose' of Compound Sodium Picosulfate Granules is a safe and efficacious preparation for colonoscopy in children aged 9-16 years.
Elderly	In the completed Ferring sponsored clinical trials 20% of patients were of $\geq$ 65 years of age. The overall incidence of treatment emergent adverse events was similar among patients of $\geq$ 65 and $<$ 65 years of age, 73% and 71% respectively.
Pregnant/breastfeeding women	
Pregnancy
 
Compound Sodium Picosulfate Granules should not be used during pregnancy unless the clinical condition of the woman requires treatment. There are no adequate and well-controlled studies with Compound Sodium Picosulfate Granules in pregnant women.
 
Breastfeeding women
 
Several drugs are excreted in human milk and caution should be exercised when Compound Sodium Picosulfate Granules is administered to a lactating woman. No formal studies have evaluated the transfer of Compound Sodium Picosulfate Granules products into human milk, or its effect on lactation or on breastfed infants.
 
The active metabolite of sodium picosulfate, BHPM is absorbed from the gastrointestinal tract. BHPM, however, remained below the limit of detection (1 ng/mL) in breast milk after both single and multiple doses of 10 mg/day. Although it is known that magnesium contained in Compound Sodium Picosulfate Granules is systemically absorbed in healthy volunteers, no information is available on the clinical use of magnesium citrate during lactation.

Patients with hepatic impairment	
Not included in the clinical development program.
 
A dosage adjustment in patients with hepatic impairment is not considered needed as sodium picosulfate is converted to its active metabolite BHPM by colonic bacteria. Sodium picosulfate and its metabolite BHPM are mainly excreted in urine.

Patients with renal impairment	Severely reduced renal function (creatinine clearance less than 30 mL/minute) is a contraindication. In patients with severely reduced renal function accumulation of magnesium in plasma may occur. Another preparation should be used in such cases.

	An analysis was performed as a post-approval commitment to the FDA. The objective was to retrospectively identify risk factors associated with the development of persistent or potential late decrease in renal function in subjects who had undergone colon cleansing with Compound Sodium Picosulfate Granules or HalfLyte in preparation for colonoscopy in Ferring Trials FE2009-01 and FE2009-02  . This retrospective analysis of renal function in subjects supports the current labelling when the product is used per label instructions as well as confirming the validity of the current renal prescribing information to physicians and subjects.
Population with relevant different ethnic origin	Phase 3 trials have been conducted in different regions involving patients of different racial and ethnic origin. Although no formal analysis has been carried out, the safety and efficacy profile of Compound Sodium Picosulfate Granules is well established in these various populations.
Patients with low body weight (BMI)	Limited data is available for treatment of patients with low body weight (BMI less than 18).

### 1.2.3 Post-authorisation Experience

The cumulative exposure to Compound Sodium Picosulfate Granules from marketing experience calculated from 01 January 1999 up to and including 31 May 2019 is estimated to 53,654,394 patients. The calculation of exposure is based upon an assumption that the number of treatments is equivalent with number of patients exposed to Compound Sodium Picosulfate Granules. One treatment consists of 2 sachets, which corresponds to an adult dose.

The frequencies of the side effects are based on post-marketing experience and as outlined in the Compound Sodium Picosulfate Granules label.

System Organ Class	Common ( $\geq 1/100$ , $< 1/10$ )	Uncommon ( $\geq 1/1000$ , $< 1/100$ )	Not known (cannot be estimated from the available data)
Immune system disorder		Anaphylactic reaction, hypersensitivity	
Metabolism and nutrition disorders		Hyponatraemia hypokalaemia	
Nervous system disorders	Headache	Epilepsy, grand mal convulsion, convulsions, confusional state	
Gastrointestinal disorders	Nausea and proctalgia	Vomiting, abdominal pain, aphthoid ileal ulcers	Diarrhoea, faecal incontinence
Skin and subcutaneous tissue disorders		Rash (including erythematous and maculopapular rash, urticaria, purpura)	

### 1.3 Study Rationale

Based on nearly 40 years' clinical experience, Compound Sodium Picosulfate Granules has a well-

established safety profile and treatment regimen that support a positive benefit/risk ratio.

According to the review of non-clinical, clinical and post-marketing data, the known adverse effects of Compound Sodium Picosulfate Granules include anaphylactic reaction, hypersensitivity, hyponatraemia, hypokalaemia, confusional state including disorientation, headache, epilepsy, generalised tonic-clonic seizure, seizure, loss of consciousness or depressed level of consciousness, syncope, presyncope, dizziness, vomiting, nausea, abdominal pain, diarrhoea, ileal ulcers, anal incontinence, proctalgia, rash (including erythematous rash, maculo-papular rash, urticaria, purpura).

According to the latest Compound Sodium Picosulfate Granules Risk Management Plan (RMP) (Ver. 2.0, 11 OCT 2019), Compound Sodium Picosulfate Granules has no important identified risks, no important potential risks, and no important missing information. Compound Sodium Picosulfate Granules's label and its package leaflet give essential information to healthcare professionals and patients on how the Compound Sodium Picosulfate Granules product should be used. Measures to minimise the risks identified for medicinal products include:

- Specific information, such as warnings, precautions, and advice on correct use, in the package leaflet and label addressed to patients and healthcare professionals;
- Important advice on the medicine's packaging;
- The authorised pack size — the amount of medicine in a pack is chosen so to ensure that the medicine is used correctly;
- The medicine's legal status — the way a medicine is supplied to the patient (e.g. with prescription) can help to minimise its risks.

Together, these measures constitute routine risk minimisation measures. In addition, information about adverse reactions is collected continuously and regularly analysed, including individual case assessment and Periodic safety update report (PSUR) assessment so that immediate action can be taken as necessary. These measures constitute routine pharmacovigilance activities. According to NMPA Regulation Order No. 81 of Ministry of Health, the safety profile of a newly approved medicine needs to be intensively monitored in a real-world setting. This study will further assess Compound Sodium Picosulfate Granules utilisation and safety profile in bowel preparation prior to X-ray examination, endoscopy or surgery when judged clinically necessary in real-world clinical practice in Chinese population.

## 2 STUDY OBJECTIVES

The objectives of this drug intensive monitoring study are to monitor and assess the safety profile of Compound Sodium Picosulfate Granules in the real world clinical practice in Chinese population, including:

- Incidence of known ADRs
- Observe occurrence of unexpected AEs/ADRs
- Incidence and risk factors of SAEs/SADRs

### 3 METHODS

#### 3.1 Study Design

This is a multi-site, prospective, non-interventional study. The subject's recruitment should not be influenced by the study protocol and should fall within the current practice.

Subjects who meet the requirements will be followed from signing the informed consent form (ICF) to about 37(+2) hours after first medication to collect AEs, medications and other relevant information with remotely contacted by pharmacist and/or hospital staff. No additional assessments or tests considered as interventional will be required. Any adverse events collected during the subject's interview will be sent to the sponsor for case processing.

#### 3.2 Medicinal Product

This study does not provide treatment, the subjects must already have been prescribed Ferring Compound Sodium Picosulfate Granules. All directions for drug usage are solely at the discretion of the subject's primary physician in accordance with his/her usual practice and should be consistent with the local prescribing information.

#### 3.3 Bias and Limitations

##### 3.3.1 *Method to Minimize Bias*

In order to limit this potential selection bias in the recruitment of subjects, the recruiter will be required to include all subjects who have been prescribed Ferring Compound Sodium Picosulfate Granules in a naturalistic fashion.

Since the AE information is collected through the report of subjects, while the missing information of AEs due to subjects failing to declare may be immeasurable.

##### 3.3.2 *Study Limitations*

This is a single arm observational study provides no comparative data. Therefore, whether the incidence of AEs in the Compound Sodium Picosulfate Granules group is higher or lower than the incidence in a non-exposed group can't be determined.

In addition, observational data may miss some relevant information or loss follow-up, the quality of data is not compatible to interventional study. The participants are voluntarily enrolled which may

have certain bias would not truly represent real world population or data.

## 4 SELECTION OF STUDY POPULATION

### 4.1 Study Population

#### 4.1.1 *Inclusion Criteria*

- 1) Agree to participate in this study and sign the ICF by subject or the legal representative.
- 2) Subjects taking the compound sodium picosulfate granules drug in real clinical practice.

#### 4.1.2 *Exclusion Criteria*

- 1) Subjects who are enrolled in other on-going studies, which prohibit any participation in this non-interventional study.

### 4.2 Withdrawal Criteria

As this is a non-interventional study, no specific withdrawal criteria are specified. Subjects are free to withdraw consent at any time. Data will be collected up to the time of withdrawal of consent, and no additional information will be collected after this time.

### 4.3 Site Selection

This study is planned to be conducted in 20 pharmacies and hospitals in China mainland.

### 4.4 Duration of Study

The overall duration of the study for each subject will be from signing the ICF to about 37 (+2) hours after the first medication. The sponsor will decide on the requirement for any follow-up of AEs persisting (see section 6.6).

The study will be considered as started when the first subject signs the ICF and will be considered as finished when the last subject's data are fully collected. The overall study duration will be approximately 2 years.

The sponsor has the right to terminate this study/close the study sites in advance after consulting the relevant regulatory agency.

## 5 STUDY PROCEDURES

The study procedure includes following steps:

1. Provide signed and dated written informed consent form prior to any procedure related to the study.
2. Evaluate subjects agreed to participate in study to make sure they meet inclusion and exclusion criteria.
3. Register eligible subjects and collect subject demographics and characteristics (gender, age, nation, height and body weight).
4. Follow up the eligible subjects 37 (+2) hours after the first medication.

For the subject who experienced AE, the following information will be collected to evaluate the safety profile of Compound Sodium Picosulfate Granules in real-world clinical practice.

- Medicinal information (administration time and dosage) and indication
- Concomitant medications
- Medical history
- Relevant lab test and its result: for the subject who experienced AE, collect relevant lab tests and its results subjects may receive as much as possible
- Safety evaluation

All stipulated events reported from signing the ICF to about 37(+2) hours after the first medication. AE information include the nature, the start date and end date, the relationship to the medicinal product, the seriousness, the outcome, and the use of corrective treatment, etc.

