**METHODOLOGY**

This is a post-marketing multi-site, prospective, non-interventional study. Compound Sodium Picosulfate granules or other similar drugs will be prescribed to the subject based on physicians' clinical judgement.

The study will collect all stipulated events reported from signing the informed consent form (ICF) to about 37(+2) hours after first medication. Contacting the subject remotely by pharmacist or hospital staff will be used to collect adverse events/reactions and other relevant information. No additional tests or examinations will be performed on subjects, no drugs will be provided to the subjects.

- The study staff will register the eligible subjects. The subjects will sign the informed consent, provide contact information. Demographic characteristics (gender, age, nation, height, weight) of subjects will be collected.
- Contact the subjects remotely 37(+2) hours after first medication to collect any adverse events and information on the Compound Sodium Picosulfate granules administration.

All adverse events collected will be sent to the sponsor for case processing.

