### 7.3 Statistical Analysis

Analyses will be performed by sponsor or its representatives. Statistical methods will be primarily descriptive in nature. No formal statistical tests will be performed.

All statistical analyses will be presented overall.

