#### 7.3.3 *Safety Evaluation*

AEs will be coded using the latest version of MedDRA and presented as “Preferred Terms (PT)

and System Organ Classification (SOC)".

Descriptive summary statistics of SAEs, AESIs and other nonserious AEs, related or unrelated to Compound Sodium Picosulfate Granules, will be presented. The main contents include the incidence, seriousness, of known ADRs/AEs and unexpected ADRs/AEs, as well as the occurrence of ADRs/AEs in specific populations. The covariates like age, gender and relevant risk factors (e.g. decreased renal function, non-compliance of drug administration or liquid intake, etc.) for the AE will be examined. Analyses and summary tables will be based upon the registry population.

Statistical analyses will present the overall results as well as separately for the specific populations.

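### Decreased renal function is to be examined as a risk factor for AEs, but the text provides for renal information only from subjects who had an AE

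*Combined protocol and SAP*

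**What the plan says.** **Collection.** For every eligible subject, Section 5 says to "collect subject demographics and characteristics (gender, age, nation, height and body weight". A second list follows, introduced by "For the subject who experienced AE, the following information will be collected to evaluate the safety profile". It covers dose and time of administration, indication, concomitant medication, medical history, laboratory results and safety evaluation. The laboratory item repeats the AE condition and asks for results only as far as they can be obtained. The synopsis (Methodology) adds: "No additional tests or examinations will be performed on subjects". It gives the purpose of the remote contact with all subjects, 37(+2) hours after first medication, as "to collect any adverse events and information on the Compound Sodium Picosulfate granules administration".

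**Analysis.** Section 2 lists "Incidence and risk factors of SAEs/SADRs" among the objectives. Section 7.3.3 names age and gender as covariates and continues: "relevant risk factors (e.g. decreased renal function, non-compliance of drug administration or liquid intake, etc.) for the AE will be examined". It also says "Statistical analyses will present the overall results as well as separately for the specific populations", while Section 7.3 says "All statistical analyses will be presented overall". Section 7.3.3 bases its tables on a registry population. Section 7.2 defines only a safety population, and the Version History records that this replaced the registry population in Version 2.0.

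**The concern.** To examine a risk factor, one must know how many subjects had it and how many did not, among those with the event and those without. If renal status is recorded only where an AE occurred, the numerator of the subgroup incidence is known and its denominator is not. A descriptive study needs that denominator as much as a comparative one does: the incidence of AEs in subjects with reduced renal function is a count divided by the number of such subjects treated.

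At stake is the renal part of the risk-factor objective. A table of renal status among AE cases fits a raised, an unchanged or a lowered risk equally well, and a reader of the report could take it for a risk-factor result.

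**Working it through.** The plan states no sample size, event count or precision target, so there is no figure to reproduce. The check has two parts.

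**1. Does any section collect renal status from AE-free subjects?**

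- Section 3.1 collects AEs, medications and further relevant information from followed subjects, but does not say what that information is.
- Section 6.7.5 permits abnormalities found before first medication to be recorded as history. It is a rule for recording AEs, not a procedure for all subjects.
- Section 6.10 lists items to be recorded whether or not an AE occurred. Non-compliance, off-label use and over- or underdose are there; renal status and medical history are not. Off-label use might pick up some contraindicated use (Section 1.2.2 gives severely reduced renal function as a contraindication), but it would not count all subjects with reduced function.
- Section 7.3.1 plans a summary of baseline clinical characteristics in the safety population. Its examples are gender, age and weight.
- Section 8 codes medical history without saying from whom it is collected.

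None does so expressly. Age, gender, nation and BMI (from height and weight) do have denominators, from the registration step in Section 5.

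**2. What can case-only data show?**

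Let m be the number of cases, a the number of cases with the factor, N the number treated, and p the prevalence of the factor among all treated subjects. Then

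RR = [a / (N p)] / [(m − a) / (N (1 − p))] = [a / (m − a)] × [(1 − p) / p].

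N cancels, and p is the quantity the plan does not collect. All inputs below are assumptions, because the documents give none.

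*Serious events, m = 5, a = 1, so a/(m − a) = 0.25:*

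- p = 2%: 0.25 × 49 = 12.25
- p = 5%: 0.25 × 19 = 4.75
- p = 20%: 0.25 × 4 = 1.0
- p = 30%: 0.25 × 2.333 = 0.58

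*ADRs, m = 30, a = 5, so a/(m − a) = 0.20:*

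- p = 2%: 0.20 × 49 = 9.8
- p = 5%: 0.20 × 19 = 3.8
- p = 16.7%: 0.20 × 5 = 1.0
- p = 30%: 0.20 × 2.333 = 0.47

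The case data cannot choose between these values.

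*What denominators would add, with N = 1,000 and p = 5% (50 with the factor, 950 without), exact 95% intervals:*

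- ADRs: 5/50 = 10% (3.33 to 21.81%) against 25/950 = 2.6% (1.71 to 3.86%). This is informative.
- Serious events: 1/50 = 2.0% (0.05 to 10.65%) against 4/950 = 0.42% (0.11 to 1.07%). This stays very imprecise.

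**The case against.** The study is descriptive, with no formal tests. Section 3.3.2 discloses that it provides no comparative data, and Section 7.3.3 promises only that factors will be examined, not that a risk ratio will be reported. Section 7.1 notes that the regulator asked for no surveillance of specific populations and adopts surveillance of the general population. The collection forms and the safety management plan cited in Section 6.10 are not in the documents and may ask for more. Even full denominators would leave the serious-event comparison weak, and it is serious events that Section 2 names. The null and inverse results above need a prevalence of 16.7% or more; at 2 to 5% every example exceeds 1, and the contraindication makes the low end plausible.

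Much of this stands, and it limits the point. It does not remove it. A descriptive subgroup incidence still needs a denominator, and at 2 to 5% alone the risk ratio for the same serious cases runs from 12.25 to 4.75, so its size is unknown even if its direction is presumed.

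A reader might infer more than the text supports:

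- *That analyses of other groups defined by medical history are planned and also lack denominators.* The gap would apply to any such group, but Section 7.3.3 names none and leaves its specific populations undefined. Of the under-represented groups in Section 1.2.2, the paediatric, elderly and low-BMI groups can be formed from data collected from everyone.
- *That the objective cannot be met.* The documents show only that renal collection from AE-free subjects is not provided for in the text.
- *That non-compliance has the same gap.* Section 6.10 requires it regardless of AE, and the synopsis collects administration information from all subjects. What remains is loose wording: Section 5 lists dosage detail under AE subjects, and Section 6.10 points to a Section 7.3.4 that no longer exists.
- *That Sections 7.3 and 7.3.3 flatly contradict each other.* Section 7.3 can be read as incomplete, because Section 7.3.3 plans overall and separate results. They still need aligning.

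**Conclusion.** The concern holds for decreased renal function. Followed as written, the plan gives renal information on cases only, and incompletely even there, with no count of treated subjects with and without the factor. Subgroup incidence and the direction of association are then not estimable. On the assumed counts, the same cases give risk ratios from 12.25 to 0.58 (serious events) or 9.8 to 0.47 (ADRs) as prevalence moves from 2% to 30%. These figures illustrate non-identifiability; they do not predict this study's results.

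The main safety results do not depend on this. Overall AE, SAE and ADR incidence, and incidence by age, gender, nation and BMI, stand, provided drug-taking is recorded for every subject as the synopsis and Sections 7.2 and 7.3.2 imply. The conclusion also assumes that no form or safety management plan outside the documents already collects renal status from all. It should be fixed because one named analysis serving a stated objective has no data behind it in the text, and the repair is cheap.

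**What to change.** Choose one.

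(a) Record known renal impairment (yes, no, unknown) from every subject at registration or at the existing 37(+2) hour contact. Do the same for any other history item that defines a specific population to be reported, and name those populations. Tabulate AE incidence by these groups, with counts and denominators, in the safety population. The cost is a few items per subject, a form change and possibly amendment approval under Section 10.1. Self-report will misclassify some renal status, serious-event comparisons will stay imprecise, and the Version 2.0 simplification is partly reversed.

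(b) Limit the risk-factor objective in Section 2 and the covariates in Section 7.3.3 to those collected from everyone. Label any renal or history data as a description of AE cases, not a risk-factor analysis. This is a wording change only, but it gives up the renal analysis.

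In either case, replace the registry population in Section 7.3.3 with the safety population of Section 7.2, align Sections 7.3 and 7.3.3 on separate presentation, and replace the obsolete Section 7.3.4 reference in Section 6.10 with a definition of non-compliance.
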